Discontinue salmeterol													
Taper/discontinue fluticasone													

Abbreviations: ACQ=Asthma Control Questionnaire; ADA=anti-drug antibody; AQLQ(S)+12=Standardized Asthma Quality of Life Questionnaire for 12 years and older; ECG=electrocardiogram; European Quality of Life – 5 Dimension 5 Level; Questionnaire ET=early termination; FeNO=fractional exhaled nitric oxide; FEV1=forced expiratory volume in 1 second; LIGHT= Lymphotoxin like, exhibits Inducible expression, and competes with Herpes Virus Glycoprotein D for Herpesvirus Entry Mediator.

1. Documentation of eligibility on all Inclusion and Exclusion Criteria is required before a subject can enter the study 30-day run-in period prior to Visit 2 (Randomization) when the subject is switched to stand alone Salmeterol and Fluticasone. Confirmation of eligibility should take place within a reasonable amount of time after the Screening Visit. If confirmation of eligibility is not available within 14 days from the date of Screening, the study Sponsor should provide approval for the subject to continue.
2. If a subject discontinues from the study/study drug, the Visit 9/ET procedures will be performed 4 weeks post last dose (±3 days).
3. A subject must be dosed with the Visit 7 (Week 8) dose no later than Day 56.
4. After Visit 2 (Day 0), visits should be scheduled relative to Visit 2 (Day 0). Visit 7 (Week 8) must not be performed later than Day 56.
5. Baseline visit to occur the day following completion of the 30-day run-in period with a window of an additional 3 days.
6. Visit 1a (Day -7) may be completed either by telephone or may be completed as an in-clinic visit, depending on the needs of the site and/or each individual subject. Visit 1a should occur with 7 days remaining in the 30-Day Run-In (-2 Day window for Visit 1a). During this phone call/onsite visit, the subject should be reminded to begin daily peak flow testing, and daily completion of their diary to capture asthma symptoms, SABA use and daily peak flow values.
7. At Visit 2 (Day 0), Visit 5 (Day 28), and Visit 7 (Day 56), pre- and post-dose vital signs will be measured: Pre-dose vital signs should be taken within 60 minutes before dosing. Post-dose vital signs should be taken at least 60 minutes after dosing, prior to discharge.
8. Height will only be recorded at the Screening Visit.

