9. Subjects should record the best result of 3 attempts daily at home. Subjects should perform daily peak flow at approximately the same time each day between 10:00 AM and 2:00 PM. Subject should also bring peak flow meter to clinic visits. If peak flow has not been completed at home by the subject on the day of a clinic visit it should be completed at the clinic during the visit.
10. In addition to ADA collection timepoints per the schedule of events, an ADA sample will be collected if an immunologically related adverse event is reported (e.g., a skin reaction, lupus-like syndrome, unexplained thrombocytopenia).
11. Select subset of sites/subjects only.
12. For females of childbearing potential. A subject is not considered to be of childbearing potential if at least 6 weeks have passed since sterilization, defined as females having undergone one of the following surgeries: hysterectomy, bilateral tubal ligation or occlusion, bilateral oophorectomy, or bilateral salpingectomy; and males who are vasectomized. Contraception is not required where females are postmenopausal (defined as 12 consecutive months of spontaneous amenorrhea and age  $\geq 51$  years).
13. On the day of Randomization when the first IP administration is required (Visit 2/Day 0), all visit procedures should be completed prior to IP administration. At the other IP administration Visit dates (Visit 5/Day 28 and Visit 7/Day 56), only the pharmacokinetic (PK), anti-drug antibody (ADA), Serum soluble LIGHT, inflammatory proteins and immunophenotyping samples must be collected prior to dosing. Other procedures can be performed as needed in the clinic on the visit day.
14. Subjects will be required to remain in the clinic for at least 60 minutes after study drug administration for adverse event monitoring.
15. Investigational product will be prepared by an unblinded pharmacist or appropriately qualified individual.
16. Immunophenotyping and PK only required if an Early Termination visit is completed. Immunophenotyping and PK not required at Visit 9/Day 98.
17. Site regular assessment of diary completion for compliance.
18. SABA use is defined as the number of individual puffs or inhalations taken by the subject.

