### **8.5 Study Entry Criteria**

Subjects are to be enrolled based on the inclusion and exclusion criteria below. The diagnosis of NEA is determined at Screening Visit 1 based upon Inclusion Criteria 2 through 5. At Baseline Visit 2, a review of all Inclusion/Exclusion criteria should be done to ensure continued eligibility prior to randomization and dosing the subject. As long as the subject qualifies as having NEA per protocol at the Screening Visit, there is no expectation that their diagnosis be re-confirmed at Baseline Visit 2, and therefore changes in eosinophil count and/or ACQ score within the period of time between Screening Visit 1 and Baseline Visit 2 would not reverse their diagnosis and would not disqualify the subject.

Although chemistry and hematology labs must be drawn as part of Baseline Visit 2 procedures,

there is not an expectation that these test results be available during the visit to re-confirm eligibility (Exclusion Criteria 12 and 13).

Per the schedule of assessments, a urine pregnancy test must be completed and show negative results at Baseline Visit 2 prior to randomization and dosing. Subjects with a positive urine pregnancy test should NOT be randomized and dosed with AVTX-002.

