- Lack of efficacy
- Adverse event
- Death
- Protocol deviation
- Physician decision
- Sponsor request
- Withdrawal by subject
- Lost to follow-up
- Other (specify). For example, pregnancy.

Subjects who require systemic corticosteroids or other non-study drug for treatment of their asthma should be considered to have lack of efficacy and withdrawn from study drug.

Subjects who meet one of the other protocol definitions of an asthma related event should also be considered to have lack of efficacy and be considered for withdraw from study drug. Instances where the Investigator feels that a subject meeting these criteria should continue receiving study drug should be discussed on a case-by-case basis with the medical monitor.

Subjects who are prematurely withdrawn from study drug should be followed up as instructed in the schedule of assessments.

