## 11.3 Special Considerations

### 11.3.1 Pregnancy

All females of childbearing potential, and males with female partners of childbearing potential, who participate in the study should be counseled on the need to utilize a highly effective method of birth control throughout the study and for 28 days following the last dose of study drug, and on the importance of avoiding pregnancy during study participation. A highly effective method of birth control is defined as one that results in a low failure rate (i.e., <1% per year) when used consistently and correctly, such as oral/injectable/inserted/implanted/ transdermal contraceptives, condom with diaphragm, condom with spermicide, diaphragm with spermicide, intrauterine hormone-releasing system or IUD, or sexual abstinence. Contraception is not required where at least 6 weeks have passed since sterilization, defined as females having undergone one of the following surgeries: hysterectomy, bilateral tubal ligation or occlusion, bilateral oophorectomy, or bilateral salpingectomy; and males who are vasectomized. Contraception is not required where females are postmenopausal (12 consecutive months of spontaneous amenorrhea and age  $\geq 51$  years).

Females and males with female partners should be instructed to contact the investigator or study staff immediately if pregnancy occurs or is suspected.

Pregnancy testing will be conducted on every female as per the schedule of assessments ([Table 1](#)). A female who is found to be pregnant at screening will be excluded from the study and considered to be a screening failure. A female who is found to be pregnant after receiving investigational product is required to be discontinued from the study and the end of study visit assessments performed as soon as possible after learning of the pregnancy.

The investigator must report the pregnancy of any female (study participant or female partner of male study participant) who becomes pregnant during investigational product treatment or within 28 days of discontinuing the investigational product (permission must be obtained from the pregnant female partner of a male subject to follow the pregnancy to conclusion and report the results). The pregnancy must be reported within 24 hours of learning of the pregnancy to the CRO

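### At Visits 5 and 7, footnote 13 allows the pregnancy test and the check for new medication and asthma events to come after the injection

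*Protocol*

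**What the plan says.** Footnote 13 to Table 1 sets two regimes. On the day of the first dose, all procedures of the visit come before the injection. On the two later dosing days, "only the pharmacokinetic (PK), anti-drug antibody (ADA), Serum soluble LIGHT, inflammatory proteins and immunophenotyping samples must be collected prior to dosing". The footnote then adds: "Other procedures can be performed as needed in the clinic on the visit day".

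Two other texts set an order relative to dosing. Footnote 7, repeated in Section 10.2.3.2.1, covers all three dosing visits: "Pre-dose vital signs should be taken within 60 minutes before dosing". Section 8.5 covers the first dosing visit only: "a urine pregnancy test must be completed and show negative results at Baseline Visit 2 prior to randomization and dosing".

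The protocol also has rules that end dosing:

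- **Pregnancy (Section 11.3.1):** "A female who is found to be pregnant after receiving investigational product is required to be discontinued from the study".
- **Systemic corticosteroids or another non-study asthma drug (Section 8.7):** such subjects "should be considered to have lack of efficacy and withdrawn from study drug". Section 9.11.4 withdraws them from the study.
- **Background or alternate therapy started after an asthma-related event (Section 10.2.2.1):** the subject leaves the study.
- **Any other asthma-related event (Section 8.7):** the subject is considered for withdrawal from study drug. If the investigator wants to continue dosing, the case goes to the medical monitor.

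**The concern.** Each stopping rule works only once the site knows the fact that triggers it. For dose 1 the protocol puts the finding-out ahead of the injection. For doses 2 and 3 it expressly releases the finding-out from any order. A site can follow footnote 13 to the letter, inject, and then record a positive pregnancy test or a steroid course from an outside clinic an hour later.

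A subcutaneous dose cannot be taken back, and SAP Section 10.5 gives a half-life of 18.0 to 27.0 days. Visit 5 follows the withdrawal of salmeterol at Visit 4. Visit 7 follows the complete withdrawal of fluticasone at Visit 6. Asthma treatment started elsewhere is plausible in both intervals. That is an inference, since the documents give no data on when events occur.

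**Working it through.** The question is one of sequence, so the main check sets the texts side by side. No figure in the plan needs reproducing.

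**1. Which facts can reach the site, and when**

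| Fact since the last visit | Rule | Route to the site | Placed before dose 2 or 3? |
|---|---|---|---|
| Pregnancy | 11.3.1: leave the study | Scheduled test; subject's own report | No. A negative result first is stated for Visit 2 only (8.5) |
| Systemic corticosteroid for asthma | 8.7: stop study drug; 9.11.4: leave the study | Medication record (source in SAP 6.2.1) | No |
| Background or alternate therapy restarted | 10.2.2.1: leave the study | Medication record | No |
| Emergency visit or admission for asthma | 8.7: consider stopping | SAE report, or investigator's event assessment at each visit (SAP 6.2.1) | No |
| Reliever rise or peak-flow fall | 8.7: consider stopping | ePRO diary, monitored by the site (10.2.2.4, 10.2.2.11) | No order stated, but visible between visits |

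SAP Section 6.2.1 lists five event criteria. Two (reliever use and peak flow) come from the diary. The other 5 − 2 = 3 (inhaled-steroid increase, systemic steroid, hospital or emergency care) come from the medication record, SAE reports or the investigator's assessment. The diary covers symptoms, reliever use and peak flow. It is not described as capturing new drugs, emergency visits or pregnancy.

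**2. Visit spacing (an outer limit, not unobserved time)**

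The windows are those in Table 1, read in visit order. Footnotes 5 and 6 confirm the windows for Visits 2 and 1a and so anchor that order.

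- Visit 4 is Day 14 ± 1 (13 to 15) and Visit 5 is Day 28 ± 3 (25 to 31). Shortest gap 25 − 15 = 10 days, nominal 28 − 14 = 14, longest 31 − 13 = 18.
- Visit 6 is Day 42 ± 3 (39 to 45) and Visit 7 is Day 56 − 3 (53 to 56). Shortest gap 53 − 45 = 8 days, nominal 56 − 42 = 14, longest 56 − 39 = 17.

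**3. Consequence per case**

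SAP Section 10.5 defines exposure as last dose date − first dose date + 28. At nominal days:

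- Stopped after dose 1: 0 + 28 = 28. With dose 2 given: 28 + 28 = 56. Difference 28 days.
- Stopped after dose 2: 56. With dose 3 given: 56 + 28 = 84. Difference 28 days.

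**The case against.** The strongest reply is that footnote 13 sets the order of procedures and removes none. It does not authorise dosing a subject known to meet a stopping rule. This stands: the stopping rules bind at every visit, and a reader who inferred that the footnote overrides them would be wrong.

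Second, Section 8.7 can only be applied if event status is known before dosing continues, so a careful investigator would ask first. This stands in part. It is an implication, and footnote 13 says in terms that other procedures may be done at any point in the visit.

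Third, the site is not blind between visits. Diary entries are monitored, subjects may report problems at each visit, and females, and males with female partners, "should be instructed to contact the investigator or study staff immediately if pregnancy occurs or is suspected". Contraception is an entry condition. This also stands. A reader might infer that the roughly 14 days before each of doses 2 and 3 go unseen. The documents do not support that, because the figure is visit spacing and two of the five event criteria are recorded daily. The diary is, however, monitored for compliance, and no route is tied to the time before the injection.

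Fourth, the Section 8.5 rule is an entry gate before randomisation, so its absence later need not be an oversight. That is fair, but the point rests on footnote 13's own words about Visits 5 and 7, not on the contrast.

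Finally, the extracted Table 1 has broken columns and lacks its upper rows, so the visits at which tests are scheduled cannot be confirmed. The pharmacy manual was not available; Section 9.3 describes it as covering syringe preparation.

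**Conclusion.** The point holds as a cheap improvement of minor weight. Apart from the listed samples and the vital signs, footnote 13 lets everything at Visits 5 and 7 follow the injection. A compliant site could therefore find a reason to withhold dose 2 or 3 only after giving it. What remains exposed is narrow: pregnancy, medication started off-site and emergency visits, when the subject has not mentioned them and the diary does not show them. Per case, this means one further injection, or 28 days of exposure by the SAP's rule.

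Three stronger readings are not supported:

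- **The checks are missing.** Pregnancy testing after baseline follows the schedule (Section 11.3.1) and events are assessed at each visit. Only their order is open.
- **Five samples are drawn before both doses.** Five is the footnote's list. Protocol Table 2 counts three immunophenotyping samples per subject and footnote 16 confines one to early termination, so that sample is probably not drawn before both.
- **The primary result is affected.** Nothing in the documents shows this, and frequency cannot be estimated from them.

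The conclusion assumes that no site instruction outside the two documents already requires these checks first. The pregnancy part applies only where a test is scheduled at Visit 5 or 7.

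**What to change.** Amend footnote 13 so that at Visits 5 and 7, before the injection:

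1. Any urine pregnancy test scheduled for a female of childbearing potential is completed and negative.
2. The site asks about new asthma medication, systemic corticosteroids and asthma-related events since the last visit, and looks at diary data through the previous day.

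Stopping at the previous day matters because of footnote 9: "Subjects should perform daily peak flow at approximately the same time each day between 10:00 AM and 2:00 PM". Waiting for that day's reading would delay dosing for no good reason. Pre-dose vital signs are already required and all other procedures stay flexible. The sponsor's medical lead should confirm the list.

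No procedure is added, so the cost is a footnote and slightly less freedom in visit flow. At Visit 7, any discussion with the medical monitor must finish by Day 56, because Section 10.1 bars later dosing. Booking that visit on Days 53 to 55 leaves room. If dosing has already ended, which the documents do not say, the wording should go into the next protocol.

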## LIST OF ABBREVIATIONS

ACQ	asthma control questionnaire
ADA	anti-drug antibody
AE	adverse event
ALT	alanine aminotransferase
AQLQ (S)+12	standardized asthma quality of life questionnaire for 12 years and older
ARDS	acute respiratory distress syndrome
AST	aspartate aminotransferase
AUC	area under the curve
AUC last	area under the serum concentration versus time curve from time zero to the last observed concentration
AUC 0-t	area under the plasma concentration time curve from time zero to the last observed concentration
AUC 0-tau	area under the curve from time zero to the time of the end of dosing interval
CGI-I	clinician global impression of improvement
CGI-S	clinician global impression of severity
COVID-19	coronavirus disease 2019
C max	maximum observed concentration
CRA	clinical research associate
CRO	contract research organization
ECG	Electrocardiogram
eCRF	electronic case report form
EC	Ethics committee
ET	early termination
EU	European Union
EUA	Emergency Use Authorization
FeNO	fractional exhaled nitric oxide
FEV1	forced expiratory volume in 1 second
FDA	Food and Drug Administration
GCP	Good Clinical Practice
HIPAA	Health Insurance Portability and Accountability Act
IB	Investigator's Brochure
ICS	inhaled corticosteroid
IC 50	50% inhibitory concentration
ICF	informed consent form
ICH	International Council for Harmonization

---

IFN	interferon
IFN- $\gamma$	Interferon gamma
IgG4	immunoglobulin G subclass 4
IL	interleukin
IL- 6	Interleukin 6
IRB	Institutional Review Board
IUD	intrauterine device
LABA	long-acting beta agonist
LIGHT	Lymphotoxin-like, exhibits Inducible expression, and competes with Herpes Virus Glycoprotein D for Herpesvirus Entry Mediator , a receptor expressed by T lymphocytes
Mab	monoclonal antibody
MedDRA	Medical Dictionary for Regulatory Affairs
NEA	non-eosinophilic asthma
PGI-C	patient global impression of change
PGI-S	patient global impression of severity
PBMC	peripheral blood mononuclear cells
PK	pharmacokinetic
PD	pharmacodynamic
PT	preferred term
SABA	short-acting beta agonist
SAE	serious adverse event
SAP	Statistical Analysis Plan
SC	subcutaneous
SD	standard deviation
SOC	system organ class
SOP	standard operating procedure
TEAE	treatment emergent adverse event
TNF	tumor necrosis factor
TNF- $\alpha$	tumor necrosis factor alpha
$t_{1/2}$	terminal half-life
$t_{max}$	time to maximum observed concentration
ULN	upper limit of normal
US	United States
VAS	visual analog scale
WHO	World Health Organization

## 6 INTRODUCTION

[figure not shown]
### 6.1 Background and Rationale in Non-Eosinophilic Asthma

[figure not shown]
Asthma is a chronic disease of the lungs characterized by airway inflammation causing swelling and excess mucous production, and as a result, patients experience difficulty breathing which can be life threatening in severe cases (Boulet et al. 2000). Asthma affects approximately 25 million patients in the US and over 300 million globally (Centers for Disease Control, 2021, IHME, 2019). There are classifications of asthma based on the inciting factors (allergic versus non-allergic) and the nature of the immune-inflammatory response (Th2 or low/no Th2) (Ray and Kolls 2017, Wenzel et al., 1999, Woodruff et al., 2009). An allergic or Th2 biased response is associated with eosinophilic classifications and related to type 2 cytokines IL-4, IL-5, and IL-13 (Lambrecht, Hammad, and Fahy 2019). Non-allergic or low/absent Th2 response is associated with neutrophilic and pauci-granulocytic classifications, which as a group are called non-eosinophilic asthma and account for 40% - 50% of all asthma patients (Douwes et al. 2002, Stokes et al., 2016).

[figure not shown]
The long-term control of asthma is typically accomplished through the use of long-acting bronchodilators in combination with inhaled corticosteroids as needed. For patients specifically with severe allergic asthma, biologic agents have been approved for treatment which target IgE (omalizumab) or the Th2-related cytokine pathways of IL-4 and IL-5 (mepolizumab, reslizumab, benralizumab, and dupilumab). The cytokine pathways identified as contributing to NEA include IL-6, IL-8, IL-17, IFN $\gamma$ , TNF $\alpha$ , and G-CSF (Lambrecht, Hammad, and Fahy 2019). For NEA patients with severe disease, there are no approved agents related to these pathways and, as such, there remains a significant unmet medical need for these patients. Previously it was demonstrated that human bronchial epithelial cells express receptors for LIGHT (LT $\beta$ R) and upon LIGHT stimulation of BEC there is a resulting broad gene expression of proinflammatory mediators, with these proinflammatory changes in gene expression being resistant to corticosteroid treatment; consistent with the clinical presentation of NEA (da Silva Antunes et al. 2015).

Human BEC cells express receptors for LIGHT (LT $\beta$ R) and upon LIGHT stimulation of BECs in vitro there is a resulting broad gene expression of proinflammatory mediators (da Silva Antunes et al. 2015), which are resistant to corticosteroid treatment, consistent with the clinical presentation of NEA. Soluble proinflammatory mediators such as IL-6, IL-8, OSM, and MCP-1 were also detected in this in vitro system. In the clinic, administration of an oral CXCR2 antagonist resulted in lowered sputum neutrophil counts and fewer mild exacerbations (Nair et al. 2012). Separately, sputum levels of soluble LIGHT positively correlated with increased sputum Th1 cytokine levels and neutrophil counts and negatively correlated with lung function (Romeo 2013). Along with soluble LIGHT detected in sputum, others have observed elevated serum levels of DcR3 in asthma patients, which are even greater during asthma exacerbations suggesting a response to elevated LIGHT levels in relation to asthma and disease activity (Kowal et al., 2019).

[figure not shown]
### 6.2 Nonclinical Experience

[figure not shown]
[figure not shown]
[figure not shown]

### 6.3 Clinical Experience

#### 6.4 Summary of Potential Risks and Benefits

### 7 STUDY OBJECTIVES AND ENDPOINTS

#### 7.1 Study Objectives

##### 7.1.1 Primary Objective

- To assess the ability of AVTX-002 to improve asthma control in subjects with poorly controlled NEA

